Statistical Methodology	Primary endpoint of the study will be 2 yr. overall survival, compared to the 60 Gy cohort of RTOG 0617 (57% 2yr OS). With an estimated improvement to 72% 2yr OS, we will need 49 patients to test for superiority of FLARE RT at 80% power and 5% Type I error. Secondary endpoints will include toxicity, and in particular CTCAE v4 grade 2 or higher pneumonitis, and 1 yr. local control, progression-free survival, and pulmonary function test decline. We will also collect plasma and urine for future correlative studies.
-------------------------	--

Table of Contents

1. Introduction
 - 1.1. Background
 - 1.2. Local Control Impacts Survival in Locally Advanced NSCLC
 - 1.3. Radiation Dose Escalation Can Improve Local Control in NSCLC, but Uniform Dose Escalation Is Detrimental
 - 1.4. FDG PET/CT Can Select For Patients at High Risk of Local Failure and Guide Dose Escalation
 - 1.5. Radiation to the Lungs Causes Pulmonary Toxicity and Limits the Deliverable Dose
 - 1.6. Current Radiation Planning Methods are Unable to Accurately Predict Which Patients Will Develop Pulmonary Toxicity
 - 1.7. SPECT/CT Perfusion/Ventilation Scans can Detect Heterogeneity in Lung Function
2. Study Objectives
3. Study Design
 - 3.1. General Design
 - 3.2. Statistical Plan
 - 3.3. Eligibility
4. Study Registration
5. Radiation Therapy
 - 5.1. Dose Specifications
 - 5.2. Localization, simulation and immobilization
 - 5.3. Target Volumes
 - 5.4. Critical Structures
 - 5.5. Treatment Planning
 - 5.6. Radiation Quality Assurance Reviews
 - 5.7. Radiation Toxicity
 - 5.8. Criteria for Removal/Withdrawal from Treatment
6. Systemic Therapy
7. Data and Safety Monitoring Plan
 - 7.1. Early Stopping Rules
 - 7.2. Interim Data Review
8. Data Management/Confidentiality

1 Introduction

This document is a protocol for a human research study. This study is to be conducted according to US and international standards of Good Clinical Practice (FDA Title 21 part 312 and International Conference on Harmonization guidelines), applicable government regulations and Institutional research policies and procedures.

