The primary endpoint of the study will be 2 year overall survival. The primary objective will be to test the superiority of 2yr OS in the FLARE RT patient cohort over the 60 Gy cohort of RTOG 0617 (57% 2yr OS) for historical control. Based on an estimated improvement to 72% 2yr OS, we will enroll at least **49 patients** to test for superiority of FLARE RT at 80% power and 5% Type I error.

Secondary Objective

[figure not shown]
- CTCAE v4 grade 2 or higher pneumonitis incidence from FLARE RT compared to historical controls (non-inferiority test)
- 1 yr local control, progression-free survival, and pulmonary function test decline
- Identification of baseline FDG PET/CT and mid-treatment FDG PET/CT imaging biomarkers for predicting patient survival
- Identification of baseline perfusion SPECT/CT imaging biomarkers for predicting G2+ pneumonitis and PFT decline
- Collection of plasma and urine samples for future correlative studies between imaging biomarkers and cytokine biomarkers of radiation response in both tumor and normal tissue

3 Study Design

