3.2. Statistical Plan

The primary endpoint of the study will be 2-year overall survival (OS). The primary objective will be to test the superiority of the 2-year overall survival rate in patients enrolled on the FLARE RT trial compared to the 60 Gy cohort of RTOG 0617 (57% 2yr OS) for historical control (11). RTOG 0617 was a randomized phase III trial for patients with unresectable non-small cell lung cancer (NSCLC), testing two radiation doses (60 Gy versus 74 Gy), and addition of cetuximab to standard chemoradiation. Results of RTOG 0617 established the current standard of care for NSCLC: concurrent chemoradiation to 60 Gy.

The expected 2yr OS and effect size of FLARE RT was derived from a weighted average of mid-treatment FDG PET responders (2 yr. OS = 92%, 41% of patient population) and non-responders (2 yr. OS = 33%, 59% of patient population) identified in a prospective patient series with 2 yr. OS rate (56%) in strong agreement with the 60 Gy cohort of RTOG 0617 (23). Based on data from a dose escalation meta-analysis (10) and the University of Michigan experience tumor dose escalation to 74 Gy in non-responders are expected to produce 4% relative improvement in overall survival per Gy (3). Combined with functional lung avoidance to reduce mean perfused lung dose from 20 Gy to 10 Gy and risk of clinical grade radiation pneumonitis, we predict a 72% 2yr OS in patients receiving FLARE RT.

The FLARE RT trial features a non-randomized design that selectively assigns patients to one of two arms based on early treatment response assessment on FDG PET/CT. In order to assess whether this selection strategy leads to superior 2yr OS compared to the historical control, we will perform a one sample proportionality test using all patients who complete either FLARE RT treatment arm (standard dose arm in responders + dose escalation arm in non-responders). In our cohort of at least 49 patients, the test is expected to detect a 2yr OS rate improvement relative to historical control from 57% to 72%, under assumptions of 5% Type I error rate ($\alpha=0.05$), 80% power ($\beta=0.20$), and 1% margin of superiority ($\delta=0.01$).

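### The primary test's success rule is not fixed (57% null, or 57% plus a 1% margin; sidedness unstated), and neither 49 nor 50 patients deliver the stated 80% power

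*Combined protocol and SAP*

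**What the plan says.** - **Study Summary, Statistical Methodology:** 2-year overall survival is compared with 57%, the 60 Gy cohort of RTOG 0617. The projected rate is 72%, and "we will need 49 patients to test for superiority of FLARE RT at 80% power and 5% Type I error". No margin is given. The Summary also sets a goal of 50 evaluable patients out of 60 enrolled.
- **Section 2, Primary Objective:** superiority is to be shown "over the 60 Gy cohort of RTOG 0617 (57% 2yr OS) for historical control", again with 49 patients, 80% power and 5% Type I error, and no margin.
- **Section 3.2, Statistical Plan:** the comparator is again 57% and the target 72%. The analysis is a one-sample proportion test in patients who complete either treatment arm. The figure of at least 49 is justified "under assumptions of 5% Type I error rate", 80% power and a "1% margin of superiority" (delta = 0.01).

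The null hypothesis is not written out in any of these places. Nor do they state sidedness, the version of the test (exact, score or Wald) or a critical number of survivors.

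**The concern.** A single-arm trial rests its primary claim on one count against one boundary, so the boundary has to be settled before the count is known. Here two statements of the objective imply 57%, and the third brings in a margin that would move the boundary to 58%. Leaving sidedness and test version open widens the range of rules that could later be called the planned one. The trial is open-label, and section 3.2 foresees interim as well as final analyses of overall survival, so the count may be partly visible before a rule is chosen.

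The power statement is also in doubt. If the margin is part of the design, 49 patients should give 80% power with it included.

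**Working it through.** **Inputs.** Null p0 = 0.57 (all three sections) or 0.58 (0.57 plus the section 3.2 margin). Alternative p1 = 0.72. Alpha 0.05, side not stated. Power 0.80. N = 49 (all three sections) or 50 (Summary goal).

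**1. Reproducing the 49.** Wald formula: n = p1(1 − p1)(z_alpha + z_beta)² / (p1 − p0)². Here p1(1 − p1) = 0.72 × 0.28 = 0.2016. One-sided, (1.645 + 0.842)² = 6.183, so the numerator is 1.246.

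- Margin added, p0 = 0.58: 1.246 / 0.14² = 63.6, so 64.
- No margin, p0 = 0.57: 1.246 / 0.15² = 55.4, so 56.
- Margin subtracted, p0 = 0.56: 1.246 / 0.16² = 48.7, so 49.

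Two-sided, (1.960 + 0.842)² = 7.849, which gives 71 against 57% and 81 against 58%. Formulas using the null variance (score) give 64 and 73 one-sided, and 81 and 93 two-sided. Continuity-corrected and arcsine versions were also tried. The only match to 49 is the one-sided Wald formula with the margin's sign reversed.

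**2. Approximate power at N = 49, true rate 72%.**

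| Reading | Wald | Score |
|---|---|---|
| 57%, one-sided | 75.6% | 70.0% |
| 58%, one-sided | 70.5% | 64.6% |
| 57%, two-sided | 64.8% | 57.0% |
| 58%, two-sided | 58.8% | 51.1% |

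**3. Exact success counts at N = 50.** The cut-off is the smallest r with P(X ≥ r | p0) at or below the limit. Power is P(X ≥ r | 0.72).

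| Null | Limit | Cut-off | Size in that tail | Power |
|---|---|---|---|---|
| 57% | 5% | 35 | 4.2% | 68.8% |
| 58% | 5% | 36 (35 gives p = 0.056) | 2.9% | 57.1% |
| 57% | 2.5% per tail | 36 | 2.1% | 57.1% |
| 58% | 2.5% per tail | 37 (36 gives p = 0.029) | 1.4% | 44.7% |

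A one-sided Wald test against 57% would accept 34 of 50 (nominal p = 0.048), but P(X ≥ 34 | 0.57) = 7.5%, so it exceeds the stated 5%.

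**4. Exact one-sided 5% at N = 49.** The cut-off is 35 under either null: p = 0.027 against 57% and 0.037 against 58%, with power 60.6%. Against 57%, 34 of 49 just fails (p = 0.052).

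**5. What the margin does alone.** With the one-sided exact test at N = 50, the two nulls disagree only at 35 survivors (70%): p = 0.042 against 57% and 0.056 against 58%. If the true rate is 72%, P(X = 35) = 68.8% − 57.1% = 11.7%.

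**6. The predicted result, 36 of 50 (72%).** One-sided exact p is 0.021 against 57% and 0.029 against 58%. Two-sided against 58%, score p is 0.045, Wald p is 0.027 and doubled exact p is 0.059. Only the last fails.

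**The case against.** The best defence is that the plan does not state two contradictory nulls. Section 3.2 also names 57%, the figure 58% is never written, and the margin sits among the sample-size assumptions. On that view it is an unexplained planning parameter, and the Summary and section 2 are shorter statements of the same design. The 49 also points to a one-sided test. The margin moves the cut-off by at most one patient at these sample sizes, and in some versions by none (exact at N = 49, score at N = 50).

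Much of this stands. A reader might infer that a result at the predicted 72% could be declared a success or a failure because of the margin. The documents do not support that: 36 of 50 succeeds under every one-sided reading, and fails only with a 58% null combined with a doubled two-sided exact p-value. A reader might also pool the counts 35 and 36 and put the chance of a disputed verdict near 24% (68.8% − 44.7%). That figure mixes the margin with the sidedness question; the margin alone accounts for 11.7%.

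The defence does not supply a decision rule. The calculation that yields 49 implies a null of 56%, which no section states and which runs against a superiority margin. The sample size therefore cannot be used to recover the intended null.

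**Conclusion.** The point holds in this form: the success rule is not fixed, and the stated power is not delivered. With an exact test at N = 50, the required count runs from 35 to 37 and power at 72% from 69% down to 45%. At N = 49 with a one-sided exact test, the count is 35 under either null and power is 61%. Against 57% or 58%, no exact, score or Wald calculation reaches 80% at 49. The sample size suggests a one-sided test but does not match the stated margin.

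This rests on reading a superiority margin as added to 57%, on a true rate of 72%, and on about 49 or 50 patients entering a test restricted to those completing treatment. The exact test is a choice made here; the plan names no version.

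**What to change.** Use one null in the Summary, section 2 and section 3.2. Either delete the margin and keep 57%, which matches the stated objective, or write 58% throughout. State an exact one-sample binomial test at one-sided 5%, give the success count, and replace the 80% power claim in all three places:

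- Null 57%: at least 35 of 50 (size 4.2%, power 69%), or at least 35 of 49 (size 2.7%, power 61%).
- Null 58%: at least 36 of 50 (size 2.9%, power 57%), or at least 35 of 49 (size 3.7%, power 61%).

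Also state that the count will be recomputed by the same rule if the final N differs. This costs wording in three places and a less favourable power figure, and needs no added patients or data. Keeping the 80% claim instead would require a larger N: even the one-sided Wald formula gives 56 against 57% and 64 against 58%.

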1.1 Background

Radiation is a major treatment option for patients with locally advanced non-small cell lung cancer (NSCLC), but current treatment regimens result in suboptimal tumor control with local failures up to 50% and 5-year overall survival (OS) of 10-20%, while carrying substantial risk of toxicity, with grade 3+ pulmonary toxicity seen in approximately 20% of patients (1-4). We propose to improve the therapeutic ratio by limiting pulmonary toxicity risk through radiation dose avoidance of functional lung defined on ventilation/perfusion SPECT/CT and increasing local control through FDG-PET/CT guided tumor dose escalation in select patients at high risk of local failure. We will explore several questions with clinical significance: (1) whether the combination of selective tumor dose escalation and functional lung avoidance synergistically impacts patient outcomes, (2) whether patient selection based on early FDG PET response can improve the potential survival benefit from PET-guided dose escalation, (3) whether radiation dose burden to functional lung better predicts clinical lung toxicity than radiation dose burden to anatomic lung, and (4) whether image parameters of spatial and functional heterogeneity in lung can select patients prior to treatment who are at highest risk of pulmonary toxicity. Answers to such questions within the scope of this pilot trial will support the launch of a multi-center trial that can definitively assess the efficacy of FLARE RT. Development of functional lung imaging heterogeneity tools and FLARE RT planning tools will enable radiation oncologists and radiologists to more precisely manage and deliver care to cancer patients.

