1.2 Local Control Impacts Survival in Locally Advanced NSCLC

Although current treatments have dose limiting toxicities including pulmonary toxicity, local control after radiation treatment is still suboptimal at around 50%. When patients die from NSCLC, both metastatic sites of disease and disease in the chest contribute to the causes of deaths (5). The lack of local control of lung tumor is clearly correlated with worse survival, and the death-rate for patients with intra-thoracic disease recurrence is similar to death-rate for patients with metastatic disease (6-8). In the CHART randomized trial testing different radiation dose/fractionation schemes, improving the local control from 20% to 29% resulted in improvement in median survival from 10 months to 28 months (9). Therefore, local control of lung tumors does impact the overall survival in patients with locally advanced lung cancer.

1.3 Radiation Dose Escalation Can Improve Local Control in NSCLC, but Uniform Dose Escalation Is Detrimental

Dose-escalation studies have shown promising local control rates when radiation dose is escalated above the standard 60 Gy in conventional fractionation. One study looking at 122 patients receiving definitive radiation treatment for lung cancer, without surgery, found that each 1 Gy increase in dose resulted in approximately 1.25% improvement in

5-year local control (3). For patients treated to 63-69 Gy, 5-year local control was 12%, versus 49% for patients treated to >90 Gy. The same trend is seen for 5-year OS, 4% versus 28% for the lower dose versus higher dose groups, respectively. Analysis of multiple patient series has found that a 1 Gy increase in dose leads to 3-4% improvement in survival and local control (10).

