Secondary objectives will feature a non-inferiority proportionality test of pulmonary toxicity incidence, defined as CTCAE v4 grade 2 or higher pneumonitis, between patients receiving FLARE RT and historical rates. Interim and final statistical analyses of the clinical endpoints (local control, progression-free survival, overall survival) will consist of Kaplan-Meier estimation and Cox proportional hazard regression. We will not conduct formal subset analyses due to insufficient statistical power. However, we will assess the relative strengths of hazard ratio estimates (and 95% confidence intervals) from a few predictors, including pre-treatment and mid-treatment imaging metrics extracted from PET/CT and SPECT/CT data. The degree of correlation amongst the variables will be evaluated. We will conduct linear regression of post-treatment lung perfusion SPECT/CT changes and decline in standard pulmonary function tests (FEV1,

DLCO, etc.). Lastly, we will perform ROC analysis to associate pre-treatment lung perfusion SPECT/CT parameters with dichotomous incidence of pneumonitis.

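### Kaplan-Meier for 1-year local control leaves death as a competing event unaddressed and, if such deaths are censored, modestly overstates local failure

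*Combined protocol and SAP*

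**What the plan says.** Section 3.2 (Statistical Plan) names one pair of methods for three endpoints: interim and final analyses of the "clinical endpoints (local control, progression-free survival, overall survival) will consist of Kaplan-Meier estimation and Cox proportional hazard regression".

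Section 2, under the secondary objective, lists "1 yr local control, progression-free survival, and pulmonary function test decline". Local control therefore has its own 1-year time point and is distinct from progression-free survival.

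The documents do not define the local-control event, say what happens to a patient who dies without local failure, or mention competing risks or cumulative incidence. Section 3.2 also rules out formal subset analyses for lack of power, and it specifies no comparison of local control between dose groups.

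**The concern.** Kaplan-Meier gives a probability for progression-free and overall survival because death counts as an event in both. For local control, death without local failure removes the patient from risk for good. Censoring that death treats the patient as someone who could still fail locally later. One minus Kaplan-Meier then describes failure in a setting without deaths, not the share of patients who fail locally.

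The protocol expects such deaths. Section 1.2 states that "both metastatic sites of disease and disease in the chest contribute to the causes of deaths", and the survival figures in section 3.2 imply substantial mortality in the first year. Local control is the mechanism on which dose escalation rests, and section 1.1 says that the results are meant to support a multi-center trial. A local-failure rate that is too high could carry over into the planning of that trial.

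**Working it through.** **Plan's own figure.** None is stated for 1-year local control, so there is nothing to reproduce for the endpoint itself. The survival inputs come from section 3.2:

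- Historical control: "compared to the 60 Gy cohort of RTOG 0617 (57% 2yr OS) for historical control".
- Prediction: "we predict a 72% 2yr OS in patients receiving FLARE RT".
- Prior series: "mid-treatment FDG PET responders (2 yr. OS = 92%, 41% of patient population") and "non-responders (2 yr. OS = 33%, 59% of patient population"), both before any gain from escalation.
- Expected survival in escalated non-responders: 4% relative gain per Gy, compounded over 14 Gy, gives 33% × 1.04^14 = 57%. Solving back from 72% gives (0.72 − 0.41 × 0.92)/0.59 = 58%. The two agree closely, and I use 57%.

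**Assumed input.** Section 1.1 speaks of "suboptimal tumor control with local failures up to 50" per cent, without a time point. I take one minus Kaplan-Meier (1−KM) at 1 year as 20-30%, and show 10% and 50% as outer values.

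**Direction.** Each increment of the cumulative incidence is the local-failure hazard times the probability of being alive and free of local failure. Each increment of 1−KM is the same hazard times the Kaplan-Meier curve for local failure alone, which is at least as large. So 1−KM is never below the cumulative incidence, and it is above it once local failures follow competing deaths. This does not depend on constant hazards.

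**Size.** Under constant, independent hazards:

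- death hazard λD = −ln(2-year OS)/2
- local-failure hazard λL = −ln(1 − F), where F is 1−KM at 1 year
- 1-year cumulative incidence (CIF) = λL/(λL + λD) × [1 − exp(−(λL + λD))]

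Worked case, OS 72% and F = 30%: λD = 0.164 and λL = 0.357. CIF = 0.357/0.521 × (1 − e^−0.521) = 0.685 × 0.406 = 27.8%, an excess of 2.2 points.

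Pooled cohort, first with every death treated as competing, then with half of the death hazard competing:

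| 2-yr OS | 1−KM | CIF, all deaths competing | Excess (points) | CIF, half competing | Excess (points) |
|---|---|---|---|---|---|
| 72% | 20% | 18.5% | 1.5 | 19.2% | 0.8 |
| 72% | 30% | 27.8% | 2.2 | 28.9% | 1.1 |
| 57% | 20% | 17.5% | 2.5 | 18.7% | 1.3 |
| 57% | 30% | 26.4% | 3.6 | 28.1% | 1.9 |

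With all deaths competing, the pooled excess is 0.8-1.3 points at 1−KM of 10% and 3.5-5.7 points at 50%.

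**By PET-response group, if results were described that way** (1−KM of 20% and 30%, all deaths competing):

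| Group | 2-yr OS | CIF | Excess (points) |
|---|---|---|---|
| Responders | 92% | 19.6%, 29.4% | 0.4, 0.6 |
| Non-responders, expected with escalation | 57% | 17.5%, 26.4% | 2.5, 3.6 |
| Non-responders, no gain | 33% | 15.5%, 23.4% | 4.5, 6.6 |

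**Sampling error.** The 95% half-width for a 30% rate at n = 49 is 1.96 × √(0.3 × 0.7/49) = 12.8 points.

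**The case against.** The strongest case on the other side has five parts.

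- **The pooled gap is small and nothing is tested on it.** It is a few points against a half-width of about 13. No hypothesis test, margin, sample size or stopping rule uses local control. This stands and limits the weight of the point. The bias is systematic, however, and more patients would not shrink it.
- **Not every death is competing.** Section 1.2 ties poor local control to worse survival, so some deaths will follow local failure. This stands. The all-deaths figures are ceilings for a given Kaplan-Meier rate, and the half-hazard columns may be nearer the truth.
- **Censoring at death is inferred.** This also stands, because the plan is silent. If deaths were counted as events instead, the estimate would be a composite, further still from local failure: in the worked case 1 − e^−0.521 = 40.6%, against 27.8%.
- **The Cox analysis is not at fault.** Correct. With deaths censored it estimates cause-specific hazard ratios, which remain valid. The problem lies only in reading 1−KM as a probability.
- **The choice is partly one of target quantity.** Cumulative incidence falls as early deaths rise, so a high-mortality group can look better controlled. This is a reason to show mortality and the cause-specific results alongside it. It does not make 1−KM the proportion of patients who fail.

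A reader might infer that the plan's comparison of escalated with standard-dose patients is distorted. The documents do not support that: no such comparison of local control is specified, and formal subset analyses are excluded. The unequal bias would matter only if results were described by response group. A reader might also cite 2-year mortality of 28-43%. The endpoint is at 1 year, where the same hazards give 15-25% dead.

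**Conclusion.** The point holds as a modest, inexpensive improvement to a secondary endpoint. Section 3.2 names an estimator that, under the usual censoring of deaths, overstates the 1-year probability of local failure. The pooled excess is at most about 1.5-3.6 points, or about 0.8-1.9 points if half of the death hazard is competing. These sizes rest on an assumed 1−KM of 20-30%, constant independent hazards and the plan's 2-year survival of 72-57%. The direction needs only that local failures occur after some deaths without local failure.

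In any description by PET response, the bias would be about 0.5 points in responders and about 2.5-3.6 points in non-responders at their expected survival. The 6.6-point figure needs non-responders to gain nothing from escalation and every death to be free of prior local failure, so it should not be read as the expected bias. The primary overall-survival test and the sample size are unaffected.

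**What to change.** In section 3.2:

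- Define the local-failure event and state how death without local failure is handled.
- Report the 1-year cumulative incidence of local failure (Aalen-Johansen estimator) with a 95% confidence interval, treating death without local failure as a competing event.
- Keep Kaplan-Meier for progression-free and overall survival.
- Label the planned Cox model for local control as cause-specific, with deaths censored. The model itself need not change.

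The cost is a sentence or two and standard software, using dates of local failure and death. There is no effect on patient numbers or visits. The one drawback is less direct comparability with published local-control figures based on Kaplan-Meier, which a supplementary Kaplan-Meier estimate, labelled as such, would meet.

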The potential survival advantage from dose escalation beyond 60 Gy was tested in a randomized trial in RTOG 0617, where patients with locally advanced NSCLC were treated to 60 Gy versus 74 Gy (11). Surprisingly, results showed that uniform dose escalation to the entire tumor volume in all patients is inferior to standard dose radiation. Local control and OS were worse in the 74 Gy arm versus the 60 Gy arm. Exact cause of the inferior outcome in the higher dose arm is unclear, but higher heart radiation dose was found to be associated with worse outcomes, and heart dose was higher in the 74 Gy arm compared to the 60 Gy arm. It is unknown if the higher heart dose is truly the cause of increased mortality, or a surrogate marker for other poor prognostic variables that were unbalanced between the two randomized arms. For example, multiple surgical series have found subcarinal lymph node involvement and multi-station mediastinal nodal involvement to be associated with poor survival in patients in lung cancer (12-14). The same effect is seen in patients treated with chemoradiation (15). Both subcarinal disease and multi-station nodal disease are associated with higher radiation dose to the heart (16). Therefore, it is possible that the higher heart dose in the higher dose arm is a surrogate for mediastinal nodal involvement, which is well known to have a negative impact on survival.

These results highlight the importance of selecting the right patient population for dose escalation, since not all patients experience local failures after 60 Gy, and only patients who would have experienced local failure would potentially benefit from escalated radiation dose beyond 60 Gy. Giving more radiation dose uniformly across an entire patient population will likely cause as much toxicity as benefit; therefore it is key to utilize strategies that can identify patients at high risk of local failure after conventional radiation doses of 60 Gy.

1.4 FDG PET/CT Can Select For Patients at High Risk of Local Failure and Guide Dose Escalation

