5.1 Dose Specifications

All patients will undergo treatment planning at initial simulation to 60 Gy at 2.0 Gy per fraction, using perfusion SPECT/CT to guide functional lung avoidance (details below). At 24 Gy (20-30 Gy acceptable), mid-treatment FDG PET/CT will be performed, and changes in tumor SUV and total lesion glycolysis (TLG) will be assessed to divide patients into metabolic responders and metabolic non-responders (details below). Patients classified as metabolic non-responders will receive dose escalation to 74 Gy, completed in 30 fractions (starting fraction 16, there will be hypofractionated dose escalation, dividing the additional 44 Gy into the remaining 15 fractions).

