5.5 Treatment Planning

Following the trial schema, we will deliver functional lung avoidance RT plans that meet pre-treatment functional lung objectives and PTV coverage. The treatment plans will be subsequently adapted to dose escalate after 3 weeks of RT based on a mid-treatment PET/CT (image after 24 Gy, between fraction 12-13 nominal) in select patients classified as FDG non-responders based on change in SUV_{max} (< 15% nominal) and total lesion glycolysis (< 15% nominal) reported from prior patient series with validation against local control and survival (23-24). FLARE RT plans will maintain 60 Gy base dose to the pre-treatment PTV, while delivering a concomitant boost to mid-treatment PTV (defined by 3 week PET/CT) during weeks 4-6 up to a total mean dose of 74 Gy in 30 fx. The 14 Gy mid-treatment PTV boost will be distributed according to relative mid-treatment FDG PET SUV. Patients who are classified as FDG responders (as defined above) at 3 weeks mid-RT will continue receiving functional lung avoidance RT to a total dose of 60 Gy, without plan adaptation.

The FLARE RT plans will be generated from unique FDG PET/CT and perfusion SPECT/CT objectives that redistribute dose at every image voxel away from functional lung regions and towards FDG-avid tumor regions. This combined differential avoidance [38] and differential tumor dose escalation [39-41] is a form of dose painting that creates continuous dose gradients rather than sharp dose gradients, which increases the robustness of FLARE RT to target motion and patient setup-induced uncertainties. In effect, the low spatial resolution PET and SPECT images acquired over many patient respiratory cycles define blurred targets and avoidance regions that help mitigate the effects of motion and risk of geographic miss during delivery of FLARE RT. Mathematically, FLARE RT objectives for FDG PET/CT-based dose escalation levels and MAA perfusion SPECT/CT-based dose avoidance levels are tabulated in the planning system as part of the cost function for plan optimization.

All FLARE RT planning clinical goals are listed in Table 2.

Structure	Clinical Goal	Type	Minor Violation	Major Violation
Pre-treatment PTV	$V_{54\text{Gy}} = 100\%$	Objective	$\geq 95\%$	$< 95\%$
	$V_{60\text{Gy}} > 95\%$	Objective	$\geq 90\%$	$< 90\%$
Mid-treatment PTV	Mean Dose = 74Gy	Objective	$\geq 66\text{Gy}$	$< 66\text{Gy}$

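### Should the plan specify 2-year survival by PET-assigned arm, and an arm term for the mid-treatment PET hazard ratios?

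*Combined protocol and SAP*

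**What the plan says.** Section 3.2 (Statistical Plan) builds the 72% target from two PET groups: responders at 92% 2-year OS (41% of patients) and "non-responders (2 yr. OS = 33%, 59% of patient population"). The gain from dose is placed in the second group: "tumor dose escalation to 74 Gy in non-responders are expected to produce 4% relative improvement in overall survival per Gy". Functional lung avoidance, given to everyone, is the other source of the expected gain; the plan gives no separate size for its effect on survival.

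The primary analysis is one one-sample test of a proportion against 57%, over both arms together. Section 3.2 then plans Kaplan-Meier and Cox analyses of local control, progression-free survival and OS. It says: "We will not conduct formal subset analyses due to insufficient statistical power". It adds hazard ratios with 95% confidence intervals for a few predictors, among them mid-treatment imaging metrics. It mentions no arm term or stratum.

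Section 5.1 sets the arm from the mid-treatment scan: "changes in tumor SUV and total lesion glycolysis (TLG) will be assessed to divide patients into metabolic responders and metabolic non-responders". Section 5.5 repeats this for "select patients classified as FDG non-responders based on change in" SUVmax and total lesion glycolysis. Section 2 lists as a secondary objective: "Identification of baseline FDG PET/CT and mid-treatment FDG PET/CT imaging biomarkers for predicting patient survival". Section 1.1 lists among the questions to explore "whether patient selection based on early FDG PET response can improve the potential survival benefit from PET-guided dose escalation".

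**The concern.** Two things look wrong.

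First, if the escalation gain is expected only in non-responders, a pooled rate does not show whether they had it. Section 1.3 reports of the earlier randomized trial of uniform escalation: "Local control and OS were worse in the 74 Gy arm versus the 60 Gy arm". A worse result in the escalated patients is therefore a real possibility. The pooled rate also moves with case mix: more responders raise it with no treatment effect at all. Too little power for a test is no reason to leave out an estimate.

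Second, the PET change that predicts survival also decides who receives 60 or 74 Gy. A hazard ratio for that change, with no account of arm, mixes the tumor's prognosis with the effect of the dose. If escalation works, the marker looks weaker than it is. If responders gain instead, it can look stronger. The planned multi-center trial could then take over a marker strength that is partly a treatment effect.

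**Working it through.** **The plan's own figures.** From the rates in section 3.2, pooled OS with no gain is 0.41 × 0.92 + 0.59 × 0.33 = 0.572, which agrees with the plan's 56% (source series) and 57% (control). With responders held at 92%, a pooled 72% needs (0.72 − 0.41 × 0.92)/0.59 = 58.1% in non-responders. A 4% relative gain per Gy over 14 Gy gives 0.33 × 1.56 = 51.5% if linear, or 0.33 × 1.04^14 = 57.1% if compounded.

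**What a by-arm estimate would show.** At N=49 and the plan's 59/41 split there are about 29 non-responders and 20 responders. Exact (Clopper-Pearson) 95% intervals:

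| Case | Count | Estimate | 95% CI |
|---|---|---|---|
| Non-responders, 58.1% met | 17/29 | 58.6% | 38.9–76.5% |
| Non-responders, linear gain | 15/29 | 51.7% | 32.5–70.6% |
| Non-responders, no gain | 10/29 | 34.5% | 17.9–54.3% |
| Responders, 92% | 18/20 | 90.0% | 68.3–98.8% |

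The linear-gain interval includes 33%. The interval at 17/29 excludes 33% but not 40% or 45% (reference rates assumed here, since the 33% comes from one series). At a true 58.1%, the lower limit clears 40% only 41% of the time and 45% only 27%. The estimate is worth displaying but would settle little.

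**How far case mix alone can move the pooled rate.** With no benefit and 26 of 49 responders, pooled OS is (26 × 0.92 + 23 × 0.33)/49 = 64.3%. At a true share of 41%, the probability of 26 or more responders is 0.06. A no-benefit pooled rate of 72% needs (0.72 − 0.33)/(0.92 − 0.33) = 66% responders. For 32 or more of 49 (65%), the probability is 0.0005. The true share could also differ from 41%, because the cut-offs in section 5.5 are nominal, but simple arm counts would reveal that.

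**The PET hazard ratio.** The simulation assumed a normally distributed PET change, a log-linear exponential hazard fitted to 92% and 33%, a cut at the 41st percentile, 3-year follow-up and a true hazard ratio of 8.0 per SD. Root mean square error (RMSE) is that of the log hazard ratio against the treatment-free value, at n=49.

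| Non-responder OS | Pooled HR, large sample | Stratified HR, large sample | Pooled RMSE | Stratified RMSE |
|---|---|---|---|---|
| 33% (no gain) | 8.1 | 8.1 | 0.43 | 0.53 |
| 51.5% | 6.3 | 7.9 | 0.48 | 0.61 |
| 58.1% | 5.9 | 8.1 | 0.54 | 0.63 |

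The distortion is real: at n=49 the pooled bias in the log hazard ratio is about −0.16 at 51.5% and −0.26 at 58.1%. It is smaller than the sampling SD of 0.43 to 0.47. Stratifying removes it, yet total error rises in every row. The stratified ratio would rest almost wholly on non-responders: 29 × (1 − 0.581) = 12.2 to 29 × (1 − 0.33) = 19.4 expected deaths by 2 years, against 20 × 0.08 = 1.6 in responders.

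A two-group contrast makes the problem look larger than this trial could detect. The ratio of cumulative hazards is ln 0.33/ln 0.92 = 13.3 with no gain and ln 0.581/ln 0.92 = 6.5 at 58.1%, a shift of 0.71 on the log scale. The standard error of such a log hazard ratio is about √(1/12.2 + 1/1.6) = 0.84, or √(1/19.4 + 1/1.6) = 0.82, so the shift is under one standard error.

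**The case for a change.** The strongest case for a change is that it costs almost nothing. Two sentences would commit the team to by-arm OS with exact intervals and to a label on the PET hazard ratio. An estimate promised in advance carries more weight than one added after the results are known, and the only sentence in the plan that touches subgroups points away from them. Section 3.2 also sets out to compare the relative strengths of predictors, so the PET change would be ranked beside variables that did not set the dose.

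Some of this stands. No section names a by-arm OS estimate or an arm term, and the pooled PET ratio should not be read as pure prognosis. But the sentence on subset analyses concerns formal ones only and does not stop anyone drawing two curves. With two named arms and Kaplan-Meier analysis already planned, analysts would show them as a matter of course. A by-arm estimate would not isolate the effect of escalation either: PET fixes the arm, there is no concurrent control, and every patient also receives lung avoidance. As for ranking, section 2 asks for markers that predict survival, and the pooled ratio does that for patients managed under this strategy.

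**Conclusion.** No change to the plan follows. The primary question in section 3.2 is whether the whole selection strategy improves 2-year OS, and the pooled test addresses it. Section 1.1 lists the selection question as one to explore and leaves definitive assessment to a later multi-center trial. By-arm OS is a gap that analysts fill sensibly, and writing it in would not alter the stated conclusion. Its interval would be about 38 points wide at 17/29. The choice between a pooled and a stratified PET hazard ratio is a fair trade-off. Stratifying removes a log bias of up to about 0.26 but raises the RMSE from 0.43–0.54 to 0.53–0.63.

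The one lasting point concerns interpretation: the pooled PET ratio describes prediction under the FLARE RT strategy. These sizes rest on the plan's 33%, 92% and 59%, which come from one series and cannot be checked against the documents, and on the simulation assumptions listed with the figures.
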